# 4 Rationale

# 4.1 Rationale for study design

Table 4-1 Rationale for study design

[figure not shown]
Study Design Aspect	Rationale
Overall (parallel design)	Parallel group design is the most efficient in studies with treatment duration of 6 months
Randomization (strata, allocation ratio)	Weighted 3:1 randomization increasing the number of participants on LTP001 thus maximizing the clinical information on LTP001 in the PAH population
Blinding	Participant- and investigator-blinding are required to avoid bias on study outcomes by knowing the treatment arm
Duration of 24-week treatment period	At earlier time points, the primary endpoint (change from baseline in PVR) may not have achieved the maximal effect, as remodeling is considered a slow process and may take time to reverse. Duration of treatment provides also evidence that effect is sustained over 6 months.
Interim analysis when approximately 20 participants completed Week 25	Allows for early decision on program or study continuation or discontinuation

**Novartis** 

minimize burden on participants, and offer them increased flexibility to participate in the study from an off-site location. This has the potential to

broaden access to clinical trials for both participants and investigators. The hybrid approach will allow participants to maintain contact with investigator, both in-person during clinic visits and through the telemedicine platform during off-site participation

4.1.1

The background therapy will be the previously used therapy by the participant. PAH-directed maintenance therapy needs to be tolerated and kept stable for 6 weeks prior to the RHC and 6MWT assessments preceding randomization, but diuretic therapy may be adjusted if needed (for details please refer to Section 6.2.1). Otherwise, the background therapy should not be changed during the study. If there is a deterioration of the participant's PAH condition requiring an escalation of concomitant PAH-specific treatment the participant should be discontinued from the study treatment (for detailed study discontinuation criteria see Section 9.1) and subsequently return for the End of Treatment assessments.

# 4.2 Rationale for dose/regimen and duration of treatment

Rationale for choice of background therapy

LTP001 will be administered once daily CCI at a dose level of mg.

In healthy volunteers, this dose has been shown to be well tolerated at single and multiple dose administrations.

CCI this dose level should be adequate and provide full efficacy. Further details are provided in the Investigator's Brochure.

# 4.3 Rationale for choice of control drugs (comparator/placebo) or combination drugs

Placebo will be used as a comparator to LTP001 to provide an unbiased control for assessing and interpreting safety data as well as clinical efficacy data generated from participants exposed to LTP001.

# 4.4 Purpose and timing of interim analyses/design adaptations

An interim analysis is planned after approximately 20 participants complete the treatment period (Week 25). For these participants, the primary endpoint, PVR, will be considered for non-binding futility and further evaluation of the totality of the data (safety, PK/PD, and other clinical endpoints along with PVR) will be considered for preliminary efficacy. PVR variability will also be evaluated during this interim for sample size re-estimation as appropriate.

Analyses for DMC review will be conducted as defined in the DMC charter. Additional interim analyses may be conducted to support decision making concerning the current clinical study, the sponsor's clinical development projects in general, or in case of any safety concerns. Blinded trial safety data will be reviewed on an ongoing basis (at least every month). Pathway and target engagement markers may be analyzed at additional time-points to gain early insights to which degree they are modulated and to allow adjustments on the selection of markers (e. g. dropping markers less sensitive then others; widening panel to further markers).

Additional information is presented in the interim analysis section (see Section 12.7).

#### 4.5 Risks and benefits

Potential risks are based on the mechanism of action, the nonclinical toxicology data and the safety data from the first in human study.

LTP001 is the first SMURF1 inhibitor to be developed. Based on current understanding of SMURF1 biology, there are no concerns directly related to this mechanism of action; and, because LTP001 is first-in-class, there are no previously identified clinical safety risks (i.e., no known class effects).

# **Preclinical data**

[figure not shown]
**Novartis** 

# Clinical data

Single doses of LTP001 were well tolerated and did not show safety signals for LTP001 in the first in human study. Adverse events under LTP001 in the single dose cohorts were abdominal pain, blood testosterone increased, diarrhea, sinus congestion and skin lesion. All AEs were mild or moderate and resolved without pharmacological intervention.

Multiple doses of LTP001 were well tolerated. **CCI** 

The risk to participants in this trial will be minimized by adherence to the eligibility criteria, close clinical monitoring, regular safety data reviews, and pre-specified rules for automatically stopping the study should unanticipated safety issues suddenly arise.

No reproductive toxicology studies have been performed for LTP001. Women of child-bearing potential will be only enrolled if they use highly effective contraception methods.

Additional details about potential risks of LTP001 can be found in the Investigator's Brochure.

### Procedural risks

Cardiac catheterization is a safe procedure when performed by an experienced medical team. But, there may be some possible risks such as bleeding, infection, and blood clots. A heart attack or a stroke can happen in very rare situations. Right heart catheterization (RHC) is regularly employed to monitor the course of PAH. RHC may be performed without radiation but for optimal placement of the catheter, the investigator can employ x-ray to double-check the positioning of the catheter when measurements are made. RHC does not employ contrast media. RHC is required to calculate PVR, which is the primary efficacy assessment and is performed at screening (up to Day 1) and at the end of treatment.

Other procedures in the study are non-invasive:

Echocardiography or ultrasound imaging of the heart uses high-frequency sound waves to view

soft tissues and does not involve ionizing radiation. Ultrasound imaging has been in widespread clinical use globally for over 20 years with an excellent safety record. There are no known adverse safety risks, but ultrasound use does produce slight bioeffects on the body as the tissue heats slightly when the acoustic waves enter the body and can also produce small pockets of gas in tissue. A hand-held transducer is placed on the skin to produce the image and its application will be limited to the region of interest (chest to perform cardiac exam) to minimize any discomfort and risk of cavitation.

Other procedures in the study are non-invasive. Participants are under observation when they perform the 6MWT.

Participants will maintain standard of care treatment for PAH. Should they require a change of PAH directed therapy due to progression of their PAH related symptoms, they will be discontinued from the study.

LTP001 is, based on its mechanism of action, not likely to interfere with immune-defense and should not impair the response to vaccines. If participants require vaccinations, e. g. against COVID-19, those can be administered according to the applicable vaccination recommendations. Also, treatment with LTP001 is unlikely to increase the risk of being infected with SARS-CoV-2, the virus causing COVID-19.

Women of child-bearing potential and sexually active males must be informed that taking the study treatment or some of the procedures, such as cardiac catheterization, may involve unknown or known risks to the fetus if pregnancy were to occur during the study, and agree that in order to participate in the study they must adhere to the contraception requirements outlined in the exclusion criteria. If there is any question that the participant will not reliably comply, they should not be entered or continue in the study.

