# **Glossary of terms**

[figure not shown]
Additional treatment	Medicinal products that may be used during the clinical trial as described in the protocol, but not as an investigational medicinal product (e.g. any background therapy)
Assessment	A procedure used to generate data required by the study
Biologic Samples	A biological specimen including, for example, blood (plasma, serum), saliva, tissue, urine, stool, etc. taken from a study participant
Clinical Outcome Assessment (COA)	A measure that describes or reflects how a participant feels, functions, or survives
Clinical Trial Team	A group of people responsible for the planning, execution and reporting of all clinical trial activities. Examples of team members include the Study Lead, Medical Monitor, Trial Statistician etc.
Coded Data	Personal Data which has been de-identified by the investigative center team by replacing personal identifiers with a code.
Cohort	A group of individuals who share a common exposure, experience or characteristic, or a group of individuals followed-up or traced over time
Control drug	A study drug (active or placebo) used as a comparator to reduce assessment bias, preserve blinding of investigational drug, assess internal study validity, and/or evaluate comparative effects of the investigational drug
Discontinuation from study	Point/time when the participant permanently stops receiving the study treatment and further protocol required assessments or follow-up, for any reason. No specific request is made to stop the use of their samples or data.
Discontinuation from study treatment	Point/time when the participant permanently stops receiving the study treatment for any reason (prior to the planned completion of study drug administration, if any). Participant agrees to the other protocol required assessments including follow-up. No specific request is made to stop the use of their samples or data.
Dosage	Dose of the study treatment given to the participant in a time unit ( )
Electronic Data Capture (EDC)	EDC is the electronic acquisition of clinical study data using data collection systems, such as Web-based applications, interactive voice response systems and clinical laboratory interfaces. EDC includes the use of Electronic Case Report Forms (eCRFs) which are used to capture data transcribed from source data/documents used at the point of care

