## 6.2.2 Prohibited medication

Participants should remain stable on their PAH-specific background therapy during the study. Unless there is intolerance to background therapy (PDE5i, prostacyclin analogues and receptor agonists, ERA, and sGC stimulators, refer to Section 6.2.1) should be kept stable during the study. Note that a required change in PAH-directed therapy due to clinical worsening of PAH should result in treatment discontinuation and appropriate management of the participant with the PAH directed therapy as per the investigators discretion and the participant's need.

In terms of treatments required for other conditions or adverse events, there are no known drug interaction signals with LTP001 at the dose level under investigation and participants should be treated as per the discretion of the investigator. Also there are no known pharmacodynamic adverse interactions with other treatments identified as yet.

Drugs which are known to prolong the QT interval are prohibited for use throughout the study duration.

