## 6.2.3 Rescue medication

Rescue medication is defined as an additional medication, or change in the dose of an existing medication.

A clinical worsening of PAH requiring a change in dose of an existing PAH-specific medication, or the addition of a new PAH specific medication, may fulfill criteria for discontinuation for study treatment (see Section 9.1.1). PAH-specific medications include: all ERAs, PDE5i, sGC stimulators and oral, intravenous or subcutaneous prostacyclin analogues and receptors agonists. For allowed modifications of PAH directed therapies and adjustments of diuretic therapy please refer to Section 6.2.1.

Use of rescue medications must be recorded on the Concomitant medications/Significant non-drug therapies eCRF after signing the informed consent.

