## 8 Visit schedule and assessments

The Assessment Schedule (Table 8-1) lists all of the assessments when they are performed. All data obtained from these assessments must be supported in the participant's source documentation.

Participants should be seen for all visits/assessments as outlined in the assessment schedule (Table 8-1) or as close to the designated day/time as possible. Missed or rescheduled visits should not lead to automatic discontinuation.

The following visits may be conducted at an off-site location as allowed by local laws and regulations: Visit 120 (Week 9), Visit 140 (Week 17), Visit 150 (Week 21), and Visit 199 (Week 29).

For all visits, assessments may occur throughout the visit window over multiple days, as needed, except where defined. For Day 1 and Week 25 visits with timed PK draws, only PK samples need to be taken post-dose.

On clinic visit days, the participant should take LTP001 during the clinic visit prior to post-dose PK samples (when applicable), when instructed by the study staff. RHC assessments and 6 minute walk test assessments should be executed at approximately the same time after drug administration each time (+/- 1 hour).

Participants who discontinue from study treatment are to return for the end of treatment visit as soon as possible, and attend the follow-up visits as indicated in the Assessment Schedule.

Participants who discontinue from study or withdraw their consent/oppose the use of their data/biological samples should be scheduled for a final evaluation visit if they agree, as soon as possible, at which time all of the assessments listed for the final visit will be performed. At this final visit, all dispensed investigational product should be reconciled, and the adverse event and concomitant medications not previously reported must be recorded on the eCRF.

[figure not shown]
The "X" in the table denotes the assessments to be recorded in the clinical database or received electronically from a vendor. The "S" in the table denotes the assessments that are only in the participant's source documentation and do not need to be recorded in the clinical database.

Table 8-1 Assessment Schedule

Period	Screening						Т	reatr	nent								EOS
Visit Name	Screening 2				Trea	tment								EC	т		EOS 
Visit Numbers 	1		100					12 0	13 0	14 0	15 0			16	0		1999
Days	-56 to -1		1					57 +5	85 +5	11 3 +5	14 1 +5			16 +			199 ±5
Weeks	-8 to -1			1			5	9	13	17	21			2	5		29

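### Protocol 4.5 takes a participant out of the study when PAH progression forces a therapy change, while other sections stop study treatment only, so the end-of-treatment catheterization may be missed

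*Protocol*

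**What the plan says.** The event is PAH progression that calls for a change of PAH-directed therapy. The protocol disposes of it in two ways.

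- **Leaves the study.** Section 4.5 (Procedural risks): "Should they require a change of PAH directed therapy due to progression of their PAH related symptoms, they will be discontinued from the study".
- **Stops study treatment.** Section 4.1.1 says that "the participant should be discontinued from the study treatment" and should "subsequently return for the End of Treatment assessments". Section 6.2.2 says that "a required change in PAH-directed therapy due to clinical worsening of PAH should result in treatment discontinuation". Section 9.1.1 lists additional PAH therapy for progression, beyond what 6.2.1 allows, among the circumstances that require study treatment to stop. It expects such participants at the end-of-treatment and follow-up visits.

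The two exits are defined terms. In the glossary, a participant who discontinues from the study "permanently stops receiving the study treatment and further protocol required assessments or follow-up, for any reason", and Section 9.1.2 repeats this. A participant who discontinues study treatment agrees to the remaining assessments, including follow-up. Under Section 8, a participant leaving the study is offered a final evaluation only if he or she agrees, "at which time all of the assessments listed for the final visit will be performed".

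On the analysis side, Protocol 12.4.4 and SAP 2.5.4 leave missing primary data unimputed. Protocol 12.4.3 and SAP 2.5.3 mark the handling of intercurrent events as not applicable.

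**The concern.** The event that triggers the conflicting rules is worsening of the disease that the primary endpoint measures. If one site reads 4.5 literally and another follows 9.1.1, whether a worsening participant has a post-baseline RHC depends on which section the site consulted. Sections 3 and 4.5 place RHC at screening and at the end of treatment, so there is no intermediate PVR to fall back on. A participant without the closing RHC contributes no change in PVR to the primary analysis, and the reason for absence is related to the value that would have been seen. In a placebo arm of about 11, one such absence is noticeable.

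**Working it through.** **1. Is it the same event?** The triggers are not worded identically. Sections 4.5 and 6.2.2 speak of a change in PAH-directed therapy; 4.1.1 speaks of escalation; 9.1.1 speaks of additional therapy beyond the 6.2.1 allowances. They overlap fully in the central case, a new PAH drug started for progression. For that case 4.5 gives one exit and the other three sections give another.

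**2. Does the difference matter for data?** Treatment discontinuation keeps the end-of-treatment and follow-up visits (glossary, Sections 8 and 9.1.1). Study discontinuation ends protocol assessments apart from an optional final evaluation (glossary, Sections 8 and 9.1.2). Section 8 does not say whether its final visit means the end-of-treatment or the end-of-study column of Table 8-1. The RHC row of that table could not be read in the copy available, so nothing is concluded from it.

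**3. What protects the data anyway?** Section 3 asks for the end-of-treatment procedures promptly whenever treatment stops early, whatever the reason. Section 10.1.3 requires SAE reporting to 30 days after the last dose. So the closing RHC may be lost under 4.5, but need not be.

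**4. Numbers in the plan.** Protocol 12.8.1 randomizes about 44 participants 3:1 with about 10% dropout.
- 44 × 0.9 = 39.6, which agrees with the planned 40 completers.
- Placebo: 44 × 1/4 = 11. LTP001: 44 × 3/4 = 33.
- The placebo prior is worth about 8 participants (Protocol 12.4.2, SAP 2.5.2). The LTP001 prior is non-informative (Protocol 12.8.1).

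**5. Illustration with assumed values.** Suppose one of the 11 placebo participants worsens, has a PVR change D above the mean of the other ten, and has no closing RHC. The full mean exceeds the mean of the ten by D/11. With the prior counted as 8 participants, and the prior mean taken as close to the mean of the ten, the shift is D/(11 + 8) = D/19. Covariate adjustment is ignored.

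| Assumed D (dyn·s·cm⁻⁵) | D/11, no borrowing | D/19, with prior |
|---|---|---|
| 200 | 18.2 | 10.5 |
| 300 | 27.3 | 15.8 |
| 400 | 36.4 | 21.1 |

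The observed placebo mean is therefore too low by about 11 to 36.

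**6. Direction.** A fall in PVR is the benefit. Losing a placebo worsener makes LTP001 look less effective; losing an LTP001 worsener makes it look more effective. One loss among 33 on LTP001 shifts that arm by D/33, which is 300/33 = 9.1 for D = 300. If the same fraction is lost in each arm (1 of 11 and 3 of 33) with the same D, the shifts cancel without borrowing: D/11 in each arm. With the prior, the placebo shift shrinks to D/19 and the LTP001 shift does not, leaving 27.3 − 15.8 = 11.5 in favour of LTP001 for D = 300. The documents do not say how losses would split.

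**The case against.** The strongest reply is that 4.5 is one sentence in a risk narrative, while the sections that govern conduct agree with one another. Section 6.7.2 also sends investigators to the treatment discontinuation criteria of 9.1. That stands, and it makes the correction easy. It does not remove an unconditional statement that uses a term the glossary defines. Section 4.1.1 itself blurs the terms: while stopping treatment, it describes the criteria in 9.1 as criteria for study discontinuation.

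Several stronger readings are tempting, and the documents do not support them.

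- **A reader might infer that a site following 4.5 collects no on-study data.** Section 3 schedules echocardiography and the 6MWT at Weeks 5 and 13 and the PROs every four weeks from Week 5. Participants who worsen after those visits already have values. The Section 3 rule on early end of treatment also covers anyone whose treatment stops, which by definition includes those who leave the study.
- **A reader might infer that later deaths and hospitalizations drop out of time to clinical worsening.** That endpoint is time to the first listed event, and starting a PAH-specific therapy for worsening is itself listed (Protocol Table 2-1, SAP 2.6.1). A gap remains mainly for a dose change of an existing drug with no other component met.
- **A reader might infer that 6.2.3 contradicts 9.1.1, because it says only that a therapy change may meet the criteria.** Section 6.2.3 covers every dose change or addition, and 6.2.1 allows some changes, such as an IV prostacyclin adjustment of up to 20%. Section 9.1.1 covers only what goes beyond those allowances. The two fit together.

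Two further limits stand. Section 9.1.1 accepts telephone contact from participants who cannot or will not attend, so aligning the terms would not by itself secure an RHC. An early RHC is also not a Week 25 value, and neither document says whether it enters the Week 25 analysis.

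**Conclusion.** The contradiction is real, is in current text, and concerns two exits that the protocol defines with different consequences for data collection. The supported conclusion is that a worsening participant may not have the closing RHC or the follow-up visit, and that any such loss would be outcome-related and left unimputed.

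The 11 to 36 dyn·s·cm⁻⁵ is an illustration of scale. It rests on one placebo loss, an assumed excess of 200 to 400, complete absence of the RHC despite Section 3, and an RHC that would have counted in the analysis had it been done. None of these is given in the documents. A claim that LTP001's benefit would be understated goes too far, because the direction depends on which arm loses participants. Time to clinical worsening is little affected. The matter should be corrected, but it does not undermine the design.

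**What to change.** Reconcile 4.5 with 4.1.1, 6.2.2, 8 and 9.1.1 so that one disposition applies when PAH progression requires a therapy change, and use discontinuation from the study only in its glossary sense. Which treatment rule is kept is a clinical decision on which no view is taken here.

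Whatever rule is kept, state that the participant remains in the study for data collection. This means the end-of-treatment procedures already foreseen in Sections 3, 4.1.1 and 9.1.1, including RHC where the participant is able and willing, and the follow-up contacts of 9.1.1.

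The cost is a protocol wording change. It adds no procedure beyond those the protocol already foresees. How an early RHC is used in the Week 25 analysis is a separate question that this wording does not settle.

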## Potential benefits

PAH is a progressive disease ultimately leading to cardiac failure and death if untreated. Preclinical data suggest that LTP001 may reduce pulmonary artery pressure and thus may control or reverse disease progression. However, LTP001 has not been used outside a Phase I study in healthy volunteers, thus, efficacy has not been proven and there is no proven direct medical benefit for participants in this study. There is also no other SMURF1 inhibitor drug tested in clinical studies. Participants randomized to the LTP001 treatment arm may benefit in the current study if LTP001 proves to be safe and effective.

